Other combinations of empagliflozin (e.g. empagliflozin on a background of SU or TZD, or empagliflozin on a background of SU and TZD) will not be assessed in this study due to the small sample size [Feasibility assessment report November 2021, data on file].

From a feasibility assessment conducted in November 2021, it is known that there are not enough study participants in the Optum and MarketScan database in each therapy line and the dual-therapy cohort was reported with the highest number of empagliflozin initiators. Therefore, a meta-analysis of the dual therapy cohorts including the data from the MarketScan MarketScan and Optum databases will be the main analysis of this study.

Due to low sample size and inadequate power, analysis of the mono- and triple therapy cohorts cannot be assessed.

Overall inclusion and exclusion criteria are listed below:

Inclusion criteria: Patients must meet all of the following criteria to be eligible for inclusion in the study:

- Patients  $\geq 18$  years old
- A diagnosis of T2DM as demonstrated by at least one qualifying diagnosis code (International Classification of Diseases (ICD)-9-CM diagnosis code of 250.x0 or 250.x2; ICD-10-CM diagnosis code of E11.x) from any encounter type recorded in the claims in the 6 months prior to the drug initiation.
- Patients initiating empagliflozin (as monotherapy, on a background of metformin, or on a background of metformin and SU) or qualifying comparator (metformin monotherapy, SU on a background of metformin, or TZD on a background of metformin and SU) during the study period.

- Have at least 6 months of continuous registration in the database prior to initiation of empagliflozin or a comparator drug

Exclusion criteria: Patients meeting any of the following criteria will be excluded from the study:

- Patients with missing or ambiguous age or sex information.
- Use of a SGLT2i, DPP-4i or GLP-1 RA in the 6 months prior to study drug initiation.
- Chronic use of insulin in the outpatient setting in the 6 months prior to the study drug initiation (definition is added to the SEAP). This criterion will help us to remove severe cases of diabetes and reduce the risk of residual confounding as diabetes is a risk factor for developing acute pancreatitis [\[R10-6620, R10-2088\]](#).

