### **9.3.3 Covariates**

Several baseline patient characteristics will be captured in the 6 months prior to the index date. Some of these covariates will be included as covariates in the propensity scores (PS) model.

- Demographics
- Comorbidity indexes: Elixhauser comorbidity index [[R14-4775](#)], Charlson comorbidity index
- Diabetes specific complications
- Comorbidities (e.g. CVD [[R21-0209](#)])
- Prior/concomitant use of other oral glucose lowering drugs
- Prior/concomitant use of other drug(s) associated with acute pancreatitis [[P08-00872](#)]:
  - $\alpha$ -methyldopa, azodisalicylate, bezafibrate, cannabis, carbimazole, codeine, cytosine, arabinoside, dapsone, enalapril, furosemide, isoniazid, mesalamine, metronidazole, pentamidine, pravastatin, procainamide, pyritonol, simvastatin, stibogluconate, sulfamethoxazole, sulinda, tetracycline, valproic acid, all trans-retinoic acid, amiodarone, azathioprine, clomiphene, dexamethasone, ifosfamide, lamivudine, losartan, lynesterol/methoxyethinylestradiol, Mercaptopurine, meglumine, methimazole, nelfinavir, norethindronate/mestranol, omeprazole, premarin, sulfamethazole, trimethoprim-sulfamethazole, acetaminophen, chlorthiazide, clozapine, didanosine, erythromycin, estrogen, L-asparaginase, pegasparagase, propofol, tamoxifen, azathioprine, sulfonamides, tetracyclines, alpha-methyldopa
- Prior/concomitant use of other medications (e.g. cardiovascular medications, full list is added in [annex 5](#))
- Other acute pancreatitis risk factors e.g. abdominal surgery, alcoholism and alcohol abuse, cystic fibrosis, gallstones and other gallbladder and biliary tract disorders, hyperparathyroidism, infection, injury to the abdomen, and lupus
- Specific lab test results (when available, see below and SEAP)
- Coronavirus (COVID-19) infection (this is applicable only to patients who have 2020 data) during the baseline period and follow up

Given the nature of the databases, it will not be possible to include exposure to over-the-counter medications as a covariate in the analysis.

The list of covariates is provided in Appendix 5 and all practical definitions and codes can be found in the statistical epidemiological analysis plan (SEAP).

Laboratory test results in a subset of patients:

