### **9.7.1 Definitions**

- Index date: Date of the first recorded claim for a qualifying prescription of an index medication as a new user.

- Follow-up: Starts from the day after the index date until the first qualifying event has been met (see [Table 2](#) and [3](#)).
- Look-back period: Patients are required to have at least 6 months of continuous registration in the database prior to initiation of an index medication. The look-back period is defined as 6 months prior to the index date and including the index date. The look-back period was specified to confirm new medication use (i.e. having a first prescription claim for empagliflozin or other oral non- incretin/non-SGLT2i-containing hypoglycaemic without use of these medications in the prior 6 months) and describe baseline parameters, such as prior medical history and medications.
- Grace period: 30 days in main analysis [[c18659315-02](#)] and 90 days [[R18-1760](#), [RRA-21430](#), [P20-07536](#)] in sensitivity analysis.

Table 2 Definitions for study end date

Reason for End of Study or censoring (earliest date of options below)	Definition for End Date
Acute pancreatitis event	Date of the first acute pancreatitis using ICD9 or ICD10 codes
Switch of index medication to another hypoglycaemic agent; see Table 3	Last date of known prescription coverage (date of last prescription fill plus days' supply minus one day) and a grace period equal to 30 days. Exposure time will not extend past the date of the first prescription claim for the newly prescribed agent*
Addition of incretin-based therapy (with continuation of index therapy)	Date of the prescription claim for the added incretin therapy
Addition of SGLT2i (with continuation of index therapy)	Date of the prescription claim for the added SGLT2i therapy
Addition of insulin (with continuation of index therapy)	Date of the prescription claim for the added insulin therapy
Addition of the within treatment line comparator index drug; see Table 3 (with continuation of index therapy)	Date of the prescription claim for the added treatment line comparator index drug
Discontinuation of index drug	Last date of known prescription coverage (date of last prescription fill plus days' supply minus one day) and a grace period equal to 30 days*
End of study data	Date of death#, Date of end of registration, Date of Study End

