### **9.7.6 Sensitivity analysis**

At least the following sensitivity analyses will be performed:

1. All analyses will be performed using an alternate outcome definition using the primary hospitalization discharge diagnosis only (ICD-9-CM 577.0 or ICD-10-CM K85 acute pancreatitis).
2. Exclude cases with ICD-10 K85.2x (Biliary acute pancreatitis) and K85.3x (Alcohol induced acute pancreatitis) and also report the percentage of these cases in overall identified acute pancreatitis cases.
3. Implement an intention-to-treat approach, where all users maintain assignment to their original treatment arm throughout a fixed follow-up period 12 months after first exposure. Users of empagliflozin or a comparator oral non-incretin/non-SGLT2i-containing glucose lowering drugs will be considered exposed from the date of first prescription claim (following a 6-month period without a prescription claim for their index medication) until earliest claim for acute pancreatitis or until one of the following censoring criteria have been met: death, end of registration, or study end. In this analysis, patients discontinuing therapy will not be censored.
4. Subgroup analyses will be performed focusing on patients with and without history of eCVD in the 12 months prior to the index date
5. It is known that Diabetic ketoacidosis (DKA) can be complicated with pancreatitis. As a sensitivity analyses, cases with prior DKA will be excluded.
6. In dual or triple therapy cohorts when the non-index medication (metformin) is discontinued or switched patients will be censored.
7. Considering grace period of 90 days for all medications.

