### **9.7.7 Handling of missing values**

The absence of a code for a condition will be interpreted as an absence of the event. If a study variable is totally missing from a database, it is excluded from the analysis of the pooled data. If a variable is missing for only some of the patients a missing data category will be added and utilized in the analysis.

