### **9.9.1 Data source**

The source claims data include limitations with respect to certainty of the capture of exposure, covariates, and outcomes. As a comprehensive insurance database, essentially all billable medical services will result in claims for reimbursement, so that the certainty of capture is tied to likelihood of a claim being submitted to the insurer.

Although duration of diabetes may represent a risk factor for the study outcome, this covariate will be incompletely captured since the patient history in the dataset is relatively short (at least 12 months, and an average of approximately 2 years), and a first claim within the database may not represent diabetes onset since the condition can be latent for some time and is typically not treated with hypoglycaemic medications at its diagnosis.

New initiators are operationally defined as patients with no use in the prior 6 months. This does not ensure, however, that patients have never used the drug of interest; the possibility remains that these patients were treated at some prior time point before they enrolled in their insurance plan.

There is potential for misclassification of dose based on healthcare utilization data, but the “days supply” field is expected to be fairly accurate. Similar concern may be present for exposure classification as well, but we expect the drug codes utilized in the data sources will appropriately represent the drug that is being classified.

Medication use in administrative healthcare databases is restricted to prescription drug medication. Consequently, the use of over-the counter (OTC) medications (e.g., OTC aspirin) is not captured. Additionally, the indication of a claim for prescription medications does not confirm whether the medication was actually taken by the patient or taken as prescribed.

It is estimated that two databases (MarketScan and Optum CDM) have about 10-15% overlap and it is not possible to identify duplicates and remove them between the two databases because patients are de-identified. It is not expected that this overlap impacts the results of this study because it will be much smaller in the study population. Furthermore, there is a sensitivity analysis to consider several scenarios of overlap in patients between the MarketScan and Optum (e.g., 0%, 10%, 20%, etc.), and 95% CIs of primary outcome will be adjusted accordingly.

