Pancreatitis reoccurs in up to 25% of patients following hospital admission for their first episode of acute pancreatitis, with smoking and/or alcohol abuse demonstrated as predominant risk factors. Smoking and alcohol use could not be measured properly in the US claims databases. Moreover, the baseline period is only 6 months which might result in misclassification of some of recurrent acute pancreatitis events as the first event.

Another important topic to take into account is death which is considered a censoring event, but this information is not well captured in claims databases.

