6.2.2 Baseline period (lookback period)

Patients are required to have at least 6 months of continuous registration in the database prior to initiation of empagliflozin or a comparator drug. The look-back period is defined as 6 months prior to the index date and including the index date. The look-back period was specified to confirm new medication use (i.e., having a first prescription claim for empagliflozin or other oral non-incretin/non-SGLT2i-based glucose lowering agents without use of these medications in the prior 6 months) and describe baseline parameters, such as prior medical history and medications.

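### The eCVD subgroups look back 12 months but patients need only 6 months of prior registration, so some eCVD patients with shorter records fall into the without-eCVD group

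*Protocol*

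**What the plan says.** Protocol 9.7.6, item 4, plans subgroup analyses in patients with and without a "history of eCVD in the 12 months prior to the index date".

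The other baseline rules use 6 months:

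- Eligibility, Protocol 9.2.2: "Have at least 6 months of continuous registration in the database prior to initiation of empagliflozin or a comparator drug".
- Look-back, Protocol 9.7.1: "Patients are required to have at least 6 months of continuous registration in the database prior to initiation of an index medication". SAP 6.2.2 agrees: "The look-back period is defined as 6 months prior to the index date and including the index date".
- Covariates, Protocol 9.3.3: "Several baseline patient characteristics will be captured in the 6 months prior to the index date". Cardiovascular disease is among the comorbidities listed there.

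Protocol 9.7.7 gives the rule for a code that is not found: "The absence of a code for a condition will be interpreted as an absence of the event".

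Item 4 does not require 12 months of registration. SAP 10.6 refers back to the protocol for the sensitivity analyses, and the visible part of SAP Annex 3 gives no separate window for eCVD.

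Two remarks in the limitations disagree with each other. Protocol 9.9.1 says that "the patient history in the dataset is relatively short (at least 12 months, and an average of approximately 2 years"), while Protocol 9.9.3 says that "the baseline period is only 6 months".

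**The concern.** A 12-month history can be read in full only for patients who were registered for 12 months. For the others, the rule in Protocol 9.7.7 turns unobserved time into evidence of no disease. The resulting error runs one way, from the eCVD group into the without-eCVD group, and depends on how long a patient was enrolled rather than on disease.

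Protocol 7 names established cardiovascular disease as a risk factor for acute pancreatitis. Undetected eCVD patients would therefore add higher-risk patients to the lower-risk subgroup and blur the contrast that item 4 is meant to show.

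There is also a practical gap. Protocol 9.8 requires two analysts to work independently and reach consistent results, but no visible rule tells them what to do with a patient who has, say, 8 months of data.

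**Working it through.** **1. The windows side by side**

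| Item | Window before index | Source |
|---|---|---|
| eCVD subgroup | 12 months | Protocol 9.7.6, item 4 |
| Required registration | at least 6 months | Protocol 9.2.2, 9.7.1 |
| Look-back | 6 months, index date included | Protocol 9.7.1, SAP 6.2.2 |
| Covariates for the propensity score (PS) | 6 months | Protocol 9.3.3 |
| No code found | counted as absent | Protocol 9.7.7 |

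A patient registered for 6 to under 12 months has up to 6 of the 12 months unobserved. If an eCVD code falls inside the observed months, the patient is classified correctly. If the only code would fall in the gap, the patient goes to the without-eCVD group. So only some short-history patients are at risk of misplacement.

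**2. Size**

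The documents give no figure for this point. Their one sample-size figure, 34,585.4 per group in Protocol 9.5, reproduces with the Farrington-Manning ratio formula (34,585.41) and does not depend on item 4. The two calculations below rest on assumptions.

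*Set A, milder.* Let s be the share of patients with under 12 months of registration (10% to 30%), m the share of eCVD patients coded only in months 7 to 12 (10% to 30%), and u the average part of that gap that is unobserved (0.5).

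- Share of eCVD patients misplaced = s × m × u.
- Low: 0.10 × 0.10 × 0.5 = 0.005, or 0.5%.
- High: 0.30 × 0.30 × 0.5 = 0.045, or 4.5%.

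With 12-month eCVD prevalence p of 15% to 35%, misplaced patients form p·s·m·u / (1 − p + p·s·m·u) of the without-eCVD group:

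- Low: 0.15 × 0.005 / (0.85 + 0.00075) = 0.1%.
- High: 0.35 × 0.045 / (0.65 + 0.01575) = 2.4%.

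*Set B, harsher.* Assume that pre-index history has a 6-month minimum, an exponential tail and mean M months, so that s = 1 − exp(−6/(M − 6)). Assume also that a short history captures 60% to 75% of eCVD, so that 25% to 40% is missed.

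| M (months) | s | Misplaced at 25% missed | Misplaced at 40% missed |
|---|---|---|---|
| 36 | 0.18 | 4.5% | 7.2% |
| 24 | 0.28 | 7.0% | 11.2% |
| 18 | 0.39 | 9.8% | 15.6% |

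Set B is the upper set for two reasons. It treats a patient with 11 months of data as no better observed than one with 6. It also centres on the 2-year average in Protocol 9.9.1 while leaving out the 12-month floor in the same sentence. If that floor applied to time before index, s would be zero. If the 2-year average includes time after index, M would be smaller and s larger. Protocol 9.9.1 does not say which is meant.

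**3. Two possible remedies compared**

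A 6-month window for everyone would miss every eCVD patient coded only in months 7 to 12. That is 10% to 30% under set A, against 0.5% to 4.5% under the present text. Under set B it is 25% to 40%, against 4.5% to 15.6%. Ascertainment becomes uniform, but more eCVD patients end up in the wrong group. Restricting item 4 to patients with at least 12 months of registration removes this source of error.

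**4. Link to matching**

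The PS uses 6-month covariates. An eCVD code found only in months 7 to 12 would count in item 4 but not in the PS, even for a patient with a full 12-month record. Protocol 9.7.2 checks balance in the matched cohort and plans no check within eCVD strata.

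**The case against.** The strongest reply is that Protocol 9.9.1 states a history of at least 12 months, so no patient is affected. This does not hold. The sentence is a limitations remark, not an eligibility criterion. It does not say that the months precede the index date, and it conflicts with the 6-month criterion and with Protocol 9.9.3. It is a further inconsistency to reconcile.

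Other objections stand, at least in part:

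- **Size.** The 60% to 75% capture rate in set B has no source in the documents, and the milder inputs give much smaller figures. No single value should be quoted as the size of the problem.
- **Pairs.** A reader might infer that the 12-month window is what makes matched pairs disagree on eCVD. PS matching balances covariates on average and does not force pairs to agree on any one of them, so pairs could disagree under a 6-month definition too. The window adds to this but is not the cause.
- **Treatment effect.** A reader might infer that the comparison of empagliflozin with sulfonylurea is biased. Protocol 9.7.2 says that the characteristics of empagliflozin initiators probably changed over the study period, so eCVD may differ by arm. But nothing in the documents shows that registration length differs by arm. What they support is some dilution of the contrast between subgroups.
- **Unseen text.** The SAP Annex 3 code files are embedded and cannot be read, so a rule there cannot be excluded.

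**Conclusion.** The inconsistency holds. As written, item 4 places some eCVD patients with 6 to under 12 months of registration in the without-eCVD group, and the error from this source runs in that direction only. The misplaced share of eCVD patients is between 0.5% and about 16% across the two assumed sets, and the documents cannot narrow this. Under the milder set, misplaced patients make up 0.1% to 2.4% of the without-eCVD group, so the effect is probably small.

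The consequence is confined to one subgroup analysis listed among the sensitivity analyses. Protocol 9.5 treats the dual-therapy meta-analysis as the sole adequately powered analysis, and neither that analysis nor its sample size uses the eCVD split. The change is worth making because it is cheap and removes an ambiguity. The study's main conclusion does not depend on it.

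**What to change.** In Protocol 9.7.6, item 4, and SAP 10.6:

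1. Restrict the eCVD subgroup analysis to patients with at least 12 months of continuous registration before the index date.
2. Report, by treatment group and database, how many patients this removes.
3. Check covariate balance within each eCVD stratum, or re-match within it, because the PS covariates cover only 6 months.
4. If a common 6-month eCVD definition is also wanted, present it as supplementary and say that it will miss more eCVD.
5. Reconcile the statement on length of history in Protocol 9.9.1 with the 6-month criterion in 9.2.2, and say whether it refers to time before index.

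The cost is a few sentences and a smaller subgroup sample: 10% to 30% of patients lost under set A, 18% to 39% under set B. If the restriction is applied after matching, pairs are lost faster. Assuming that the two members' registration lengths are independent, the share of intact pairs is (1 − s)², which is 0.81 at s = 0.10 and 0.37 at s = 0.39. Restricting first and then matching avoids this. No new data are needed.

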### **9.7.7 Handling of missing values**

The absence of a code for a condition will be interpreted as an absence of the event. If a study variable is totally missing from a database, it is excluded from the analysis of the pooled data. If a variable is missing for only some of the patients a missing data category will be added and utilized in the analysis.

### **9.7.8 Safety Analysis**

Not applicable based on secondary use of data without any potential that any employee of BI or agent working on behalf of BI will access individually identifiable patient data.

## **9.8 QUALITY CONTROL**

The quality control, review, and monitoring plan are summarized below. Greater details are documented in the NIS-DMRP.

All measures created, cohorts developed, statistical analyses implemented, and tables completed will be conducted by two analysts independently. After completing the whole analysis, each analyst will undergo quality control review for the other analyst's work. The final results need to be consistent results from both analysts.

This protocol will be strictly followed in the study. All changes to this protocol will be documented in protocol amendments.

All programs for data management and data analyses written by study statistician(s) will be self-documenting with comments about the data handling process, the population selection and the analysis performed by the program. The documentation will be sufficient for another statistician to be able to repeat the program. A statistician other than the one who writes the program will carry out quality control checks of these programs. The programming quality control (QC) will be performed for all programs related to the database, its individual datasets from different registers and statistical analyses. The QC will be documented with the following information:

- Name of the program
- Purpose of the program
- Name of the programmer
- Validation status and date of validation
- Updates and dates of updates
- Name of the QC statistician
- QC findings or comments
- Date of QC

The statistician responsible for the QC of a program will ensure that:

- The correct dataset and population is used
- The analysis is carried out according to the SEAP
- The analysis results are consistent
- The output is in line with the table shells in the SEAP
- The analysis can be interpreted in both statistical and clinical terms

All QC findings by the QC statistician will be documented, and corrections are made to the programs accordingly. All changes are documented as updates to the original program.

The raw dataset and statistical programs used for generating the data included in the final study report will be kept in electronic format and be available for auditing and inspection.

